Patients assigned to the intervention group receive an audio-reminder, generated by a smartphone. For patients with Smartinhaler, the inhalation times are entered on the Smartinhalerlive.com website by the investigator. These are generated by an app on the smartphone. For patients with POEMS, the inhalation times are entered also by the investigator directly as an alarm clock on the smartphone. Patients were allowed to choose the inhalation times themselves, depending on their personal habits and daily routine, and it was possible to define a time for the working days and a time for the weekend. In both cases, the generated reminders have to be stopped by the patient and will have no link to the inhalation actuation. Moreover, these patients receive support calls when the use of rescue medication doubles or if the inhaled medication is not inhaled as prescribed for more than two consecutive days. They also receive a feedback on their adherence at each visit, especially for the results of the POEMS.

Patients assigned to the control group have no reminder and will receive no further support regarding the adherence of their inhaled medication.

CALCULATION OF SAMPLE SIZE

“Time to next exacerbation” is subject to the power calculation. A previous study has shown that 30% of COPD patients are readmitted again within six months because of an exacerbation[47]. We expect that 12% of the patients in the intervention group will have an exacerbation. This corresponds to a hazard ratio (intervention/control) of 0.36. Assuming a sample size of 70 subjects for each study group, there is a power of 80% to detect a HR of 0.36 based on a one-tailed test. The calculation is based on the assumptions mentioned above and on a one-tailed significance level of 5%. Additional 14 subjects (7 for each study group) have been added to account for dropouts. Therefore, 154 subjects will be investigated in this study.

MEASUREMENT OF OBJECTIVE ADHERENCE

Adherence is measured in both groups using Smartinhalers and POEMS as outlined above. Daily measurements are started after the baseline visit (T0) and are continued until the end of the study (visit T3).

Recorded data are uploaded daily at 00:00 to a web-based database via a wireless connection. Participants are asked to take their medication at the first visit in order to ensure the correct handling and usage of the Smartinhaler. Once the devices are installed on the inhalers, patients can use their medication as usual.

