Currently, no monitoring devices exist that were specifically developed for monitoring the adherence of the newly introduced inhalation-device Ellipta®. To assess adherence in patients undergoing treatment with Ellipta® a Smartinhaler with a placebo-device is handed out and patients are instructed to trigger a puff of the placebo every time when they inhale their active treatment. This procedure allows an indirect recording of date and time actuation of the Ellipta® inhaler.

For inhalation with powder capsules (Breezhaler and HandiHaler), POEMS are used. The capsules are pre-filled for the following 2 weeks with a patient's individualized prescription plan (mostly one time daily inhalation of capsule contents). The multidose punch cards are filled manually by a pharmacist. The participants with Breezhaler and HandiHaler will receive one multidose punch card for every 2 weeks. Every time the patients break a loop for taking the capsules, date and time are recorded on a microchip, which can be read when the patients bring back the empty punch card.

DATA COLLECTION AND OUTCOME MEASURES

The primary outcome of this study is “time to next asthma or COPD exacerbation”, defined as acute-onset worsening of the patient's condition beyond day-to-day variations requiring interaction with a health care provider[48], which may occur during the index exacerbation or follow-up. Data collections about this outcome are assessed after two, four and six months (number of exacerbations since last visit with exact period of exacerbation and number of exacerbation with hospitalization). If patients are not able to give information about the time of exacerbation, treating physician is contacted.

Sociodemographic variables such as gender, civil status, age, education level and employment status are obtained by a generic questionnaire at the baseline visit. Furthermore, body mass index (BMI), smoking status, as well as pack years (py) are assessed during this visit. In addition, disease-related questions such as allergies,

comorbidities, current medication and number of exacerbations in the previous twelve months are recorded including hospitalizations and emergency department attendance.

This project focuses on the implementation of a prescribed dosing regimen. Objective adherence will be analyzed according to the following widely used definitions[49]:

- Taking adherence: (Number of puffs inhaled during 24h/number of puffs prescribed during 24h) x 100.

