- Timing adherence: (Number of correct dosing intervals during 24 hours/number of dosing intervals during 24 hours) x100; correct dosing intervals are prescribed intervals $\pm 25\%$:
 - o For once daily dosing: $24h \pm 25\% = 18-30h$
 - o For twice daily dosing: $12h \pm 25\% = 9-15h$
 - o For three daily dosing: $8h \pm 25\% = 6-10h$
- Gaps: (Number of days without inhalation during the whole study period/number of days in same time period) x 100.
- Maximal gap length: Number of consecutive days of the longest period of time without inhalation.

Different lung function tests are performed at baseline, after two, four and six months to assess changes in lung function (FEV₁, FVC, FEV₁/FVC), diffusion capacity, NO-measurements and CO-measurements.

To evaluate the inhalation technique, participants demonstrate at baseline and at every follow up visit how they actually use their device at home. For this purpose, placebo devices are used to prevent overdosing. Correctness of inhaler use is assessed using pre-defined checklists for each inhaler type based on user guidelines and instruction package inserts from the manufacturers[50-55]. Correct inhaler usage is defined as correct performance of every step on the checklist. Incorrect inhaler usage is defined as one or more steps done incorrectly. A total score is calculated (incorrect application =0, correct application =1) and applied to every step. Possible errors are corrected by verbal instruction and visual demonstration. For ethical reasons the correction was performed in both groups. Patients demonstrate their inhalation technique until it is performed correctly.

To assess patients' beliefs about the need of the prescribed medication and their concerns about the potential adverse consequences of taking it, the BMQ is used at baseline.

Changes in quality of life are assessed at baseline, after two, four, six months using different disease-specific questionnaires: SGRQ, CAT and ACT. To assess general quality of life, SF-36-questionnaire is used.

STATISTICAL ANALYSIS

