Statistical analyses, including descriptive statistic and survival analyses, are done using the software R (RStudio®, Boston, USA) and SPSS (IBM Corporation, Armonk, USA). Statistical significance is set at the 5% level. Time to next exacerbation is compared using the Kaplan-Meier method and Cox proportional hazard model. Results will be reported as HR (hazard ratio) with corresponding 95% confidence interval (CI) and p-value. A hazard ratio smaller than one is expected. This means that the intervention group will have a smaller risk for exacerbations. Associations between time to between exacerbation and independent predictors will be analyzed (taking adherence, timing adherence and gaps without

inhalation). Comparisons of secondary parameters are done using t-tests or chi-square-tests (or their nonparametric equivalents if continuous data are not normally distributed).

HANDLING OF MISSING DATA AND DROP OUTS

Patients will be rated as drop out when they will be excluded from the study at their request or if they will be no longer able to participate in the study until the final visit at six months. Patients, who will not be able to undergo all clinical examination during the follow-up visits, will remain in the study. Multiple imputation methods will be used to impute missing data with less than 25% missing values, which is typically more efficient than complete cases analysis when covariates have missing values[56].

ETHICS AND DISSEMINATION

This study is conducted according to the Helsinki Declaration and according to the good clinical practice guidelines. The study participation of the patients is voluntary and can be revoked at any time without specification of reasons and will have no disadvantages for their future medical care. The study was approved by the Ethics Committee of Nordwest- and Zentralschweiz (registry number: EK- 269/13) and was registered in the <https://clinicaltrials.gov/trials> database (NCT02386722). The results of this study will be disseminated via seminar and conference presentations and in academic peer reviewed journals.

DATA SECURITY/DISCLOSURE OF ORIGINAL DOCUMENTS

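### Gaps are counted to the end of the study but used to predict time to exacerbation, so days after the event enter the predictor; taking and timing adherence have no stated window

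*Combined protocol and SAP*

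**What the plan says.** The primary outcome, under Data Collection and Outcome Measures, is stated as follows: "The primary outcome of this study is “time to next asthma or COPD exacerbation". Statistical Analysis then adds a second use of that outcome: "Associations between time to between exacerbation and independent predictors will be analyzed (taking adherence, timing adherence and gaps", the last of these meaning days with no recorded use.

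The three predictors are defined under Data Collection and Outcome Measures:

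- The first is a daily ratio of puffs: "Taking adherence: (Number of puffs inhaled during 24h/number of puffs prescribed during 24h) x 100".
- The second is a daily ratio of dosing intervals, again with no summary period: "Timing adherence: (Number of correct dosing intervals during 24 hours/number of dosing intervals during 24 hours) x100".
- The third is the only one with an explicit period: "Gaps: (Number of days without inhalation during the whole study period/number of days in same time period) x 100".

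Measurement of Objective Adherence says "Daily measurements are started after the baseline visit (T0) and are continued until the end of the study (visit T3"). At each visit the investigators collect the "number of exacerbations since last visit with exact period of exacerbation and number of exacerbation with hospitalization", so follow-up and recording continue past a patient's first exacerbation. The plan gives no lag, landmark, time-dependent covariate or cut-off at the event for this analysis.

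**The concern.** A predictor of time to an event should be known before the event. Whole-period gaps are not. For a patient who exacerbates on day 30 of about 182, 152 of 182 days (84%) of the predictor are recorded after the outcome. Any effect of the exacerbation on recorded inhaler use then looks like an effect of adherence on exacerbation.

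The protocol gives routes for such a change:

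- In the intervention arm, participants "receive support calls when the use of rescue medication doubles or if the inhaled medication is not inhaled as prescribed"; the second trigger applies once the lapse exceeds two days in a row. Doubled rescue use may well accompany an exacerbation.
- In both arms an exacerbation by definition involves contact with a health care provider, and the usual physicians control prescriptions (Study Design and Procedures).
- Some exacerbations lead to hospitalisation. The plan does not say whether inpatient days without a recorded inhalation count as gaps. If they do, the event itself creates the predictor value.

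The closing section on expected results anticipates that better adherence will lengthen time to exacerbation. This is the only planned analysis that relates measured adherence to that outcome, so it is likely to be read as support for the link. The direction of any bias depends on what patients do after an event, so a reader could not correct for it.

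**Working it through.** **Inputs from the plan.** Calculation of Sample Size gives 6-month event proportions of 30% (control) and 12% (intervention), 70 per group plus 7 for dropout, total 154. These proportions reproduce the plan's hazard ratio: ln(0.88)/ln(0.70) = 0.358, or 0.36. With 70 × 0.30 + 70 × 0.12 = 29.4 events, Freedman's formula at one-sided 5% gives 81.8% power, close to the stated 80%. The present point does not depend on that power figure.

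**Simulation inputs.** The mean event proportion is (30% + 12%)/2 = 21%, and 154 × 0.21 ≈ 32 events over 182 days. *Assumed, not in the documents:* each patient's gap-day probability follows Beta(2.5, 7.5), with mean 25% and SD √(0.25 × 0.75/11) = 13.1 points. Event times are exponential. Gaps have no effect on the hazard. Each scenario has 2,000 trials and a single-covariate Cox model at two-sided 5%.

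**How far the predictor moves.** A 10-point shift lasting d days changes a patient's whole-period percentage by 10 × d/182:

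- 14 days: 0.8 points
- 28 days: 1.5 points
- 56 days: 3.1 points
- from day 30 to T3: 10 × 152/182 = 8.4 points

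Against an SD of 13.1 points, brief shifts matter little and lasting ones a great deal.

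**False-positive rates for whole-period gaps** (10-point fall / rise; hazard ratios per 10 points):

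| Change after the event | Rejection |
|---|---|
| None | 4.6% (3.9% in a repeat run), HR 0.99-1.00 |
| 14 days, all event patients | 5.5% / 5.0% |
| 28 days, all | 8.1% / 9.2% |
| 56 days, all | 14.1% / 17.7% |
| To T3, all | 49.5% / 51.7%, HR 0.74 / 1.27 |
| To T3, half of event patients | 17.4% / 17.6% |
| To T3, 29% of event patients | 7.3% / 8.9% |

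The 29% is the intervention arm's share of events: 77 × 0.12 = 9.2 of 32.3.

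**Sensitivity to the assumed spread of adherence.** With Beta(5, 15) (SD 9.4 points) the lasting shift gives 76-77%, 56 days 28-29% and 28 days about 11%. With Beta(1, 3) (SD 19.4 points) the figures are 23-28%, 7-12% and about 6%.

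**Inpatient days.** Suppose half of event patients have 10 inpatient days with no recorded inhalation (assumed). Each such patient's percentage rises by about 10 × 0.75/182 = 4.1 points, and the false-positive rate is 13.0%. With mean gap days of 10% (Beta(1, 9), SD 9.0 points) the rise is 10 × 0.90/182 = 4.9 points and the rate is 25.6%. Seven days give 6.3% and 15.2%.

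**Separate check under other assumptions.** This used 140 patients, Beta(2, 8) and a proportional change to study end. Halving gaps after the event gave HR 0.67 (56% false positives), no change 0.99 (4%) and doubling 1.52 (93%). If the change lasted only 30 days, halving gave 6% and doubling 24%.

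**Alternatives in the null simulations:**

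- Fixed percentage simply cut at event or censoring: 7.0-9.2%. The length of the measurement period then still depends on the outcome.
- Time-dependent, preceding 28 days with a 3-day lag: 3.5-5.8%.
- Landmark at day 61 (T1): 3.5-5.5%.
- Time-updated cumulative percentage from T0 to the day before each risk time: 4.5-6.1% in the separate check.

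**Events retained.** With λ = −ln(0.79)/182 = 0.001295 per day, events after day a number 154 × (exp(−λa) − 0.79). This gives 26.3 for a = 31 (28-day window plus lag), 20.6 for a = 61 (landmark) and 30.9 for a = 7 (cumulative, leaving out the first week).

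**The case against.** The strongest reply is that the size of the problem is unknown and the large figures need extreme conditions. A rate near 50% requires every event patient in both arms to shift by 10 points until T3, and nothing in the documents shows this. Shifts of 14 to 28 days give 5-9%. Adherence feedback is given at every intervention visit, and calls for missed doses follow missed doses, so neither is triggered by an exacerbation. The rescue-use call exists only in the intervention arm, where a lasting shift gives 7-9%. The inpatient scenario assumes a hospitalisation share and a length of stay that the plan does not give. All of this stands and limits the magnitude. It does not remove the defect, because contact with a provider and hospital stays apply to both arms.

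The wording is also open. The association sentence names no model, and its outcome is garbled. If it means time between exacerbations, days after one event are at-risk days for the next. Even so, a whole-period measure contains days that lie in the future at each risk time. For taking and timing adherence the fault is only that the summary window is unstated.

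The event count is uncertain too. The plan's power basis is 140 patients (29.4 events), Study Design and Procedures mentions 169 participants, and the 30% is a readmission figure while the outcome is broader. These points change the precision of the illustration but not the mechanism.

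Finally, this is a secondary association. That is correct and is why the point does not rank higher.

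**Conclusion.** The concern holds. Followed as written, the plan puts post-event days into a predictor of the event, and it leaves the same error open for taking and timing adherence. The bias is conditional: none if recorded use is unchanged after an exacerbation, little for a change of about two weeks, and substantial for changes of two months or more or if inpatient days count as gaps. Under the main assumptions the false-positive rate runs from about 5% to about 50%, and the hazard ratio can move either way (0.74 to 1.27 per 10 points) when the truth is 1. These figures rest on an assumed spread of adherence and assumed post-event shifts, because the documents give neither. The randomised comparison of time to exacerbation and the sample size are not touched. The analysis should be re-specified before the data are examined.

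**What to change.** For this analysis, replace whole-period gaps with adherence recorded strictly before each risk time, using one of these:

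- **Time-dependent covariates in a counting-process Cox model.** Use taking adherence, timing adherence and percentage of gap days over a stated recent window with a short lag (for example, the preceding 28 days with a 3-day lag), or cumulatively from T0.
- **A T1 landmark.** Use adherence in months 0-2 to predict events in months 2-6 among patients still event-free at T1.

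State the window for all three measures, say how inpatient days are counted, and write the outcome of this analysis unambiguously. Do not simply truncate a fixed percentage at the event. The whole-period definition can stay for describing adherence.

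The cost is a few sentences and some programming. The devices already record date and time, and exacerbation periods are already collected. Onset dates come from two-monthly visits or the treating physician, which is a reason for a lag. Early events are lost: about 26 of 32 remain with the lagged 28-day window, about 21 with the landmark and about 31 with the cumulative version.

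Power also differs. With an assumed true hazard ratio of 1.4 per 10 points and stable adherence, it was about 65% (cumulative), 54% (28-day window) and 51% (landmark). A second run with a true effect gave 65%, 58% and 53%. The choice of window can be left to the investigators, provided it is fixed in advance.

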The objective of this study is to investigate the adherence to inhaled medication in asthma and COPD patients with an innovative methodology using specific electronic devices, which are able to provide data about the timing of inhaler action. Moreover, we want to assess the effect of an acoustic reminder and a close supervision by a pharmacist on the adherence, course of diseases and quality of life.

METHODS AND ANALYSIS

PARTICIPANTS AND RECRUITMENT

In- and outpatients with a diagnosis of asthma bronchiale or COPD from several hospitals in the Basel region illustrated on table 1 and patients treated by pulmonologists in private practice are screened for eligibility. In addition, advertisement is made using posters, flyers, as well as on ad-screens (Cantonal Hospital Baselland Liestal and Bruderholz) including the most important information about the study. Advertisement is also placed in local newspapers.

Table 1 Recruitment locations and related recruitment types

Hospital	Location	Type of recruitment
Cantonal Hospital Baselland	Liestal, Switzerland	- Screening of hospitalized

		patients
Cantonal Hospital Baselland	Bruderholz, Switzerland	- Screening of emergency department
Claraspital	Basel, Switzerland	- Screening of DRG-lists
Clinic Barmelweid	Barmelweid, Switzerland	- Screening of DRG-lists
Gesundheitszentrum Fricktal AG	Rheinfelden, Switzerland	- Collaboration with pulmonology department
		- Collaboration with pulmonology department
		- Collaboration with pulmonology department
		- Collaboration with pulmonology department

DRG, Diagnosis Related Groups.

In- and exclusion criteria initially are checked via telephone or during hospitalizations or practice visits. Eligible patients are invited for an initial training course. Before the study start, the investigator provides written and verbal information on content and duration of the study. In case of willingness to participate, patients have to sign an informed consent.

PATIENT INCLUSION CRITERIA

- males and females aged ≥ 18 years with
- asthma- and/or COPD diagnoses and
- prescribed daily inhaled medication with
- at least one exacerbation in the previous twelve months

PATIENT EXCLUSION CRITERIA

- patients with malignancies and/or other severe diseases or
- insufficient German language
- pregnant or lactating women

Enrolment started on January 2014 and will end as soon as at least 154 individuals are included in the study.

STUDY DESIGN AND PROCEDURES

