Visits take place at baseline (T0), after two (T1), four (T2) and six months (T3). Each visit includes a spirometry (EasyOne Pro, ndd Medizintechnik AG, Zurich, Switzerland), measurement of diffusion capacity (EasyOne Pro, ndd Medizintechnik AG, Zurich, Switzerland), exhaled nitric oxide (NIOX MINO®, Aerocrine AB, Sweden) and carbon monoxide (piCO⁺ Smokerlyzer, Bedfont Scientific Ltd., Kent, UK) measurements. To detect false device applications, each patient is asked to demonstrate the inhalation technique with all prescribed devices to the investigator using a placebo device (to avoid overdosing). Moreover, participants have to fill out the COPD Assessment Test (CAT)[41], the Asthma Control Test (ACT)[42], the St. George’s Respiratory Questionnaire (SGRQ) and the Short Form (SF)-36[43, 44] to assess quality of life at baseline, after two, four and six months. To assess patients’ beliefs about the necessity of the prescribed medication and their concern about the potential adverse consequences of taking it, the Beliefs about medicines Questionnaire (BMQ) is used at baseline[45, 46]. During these visits we also obtain information about exacerbation since the previous visit.

RANDOMIZATION

After having given written informed consent eligible subjects are randomly assigned either to the intervention or to the control group. The intervention group is provided with an acoustic reminder for inhalation and receives support calls when the medication is not taken as prescribed while the control group receive no further support regarding the adherence. A randomization list with study group allocation is generated using R (RStudio®, Boston, USA). Randomization procedure is provided in block size of two. Therefore, examinations between study groups are sequent. This reduces the risk of a season effect between study groups. The patients are not aware of which group they have been randomized to (single-blinded).

CLINICAL INTERVENTIONS

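### Secondary outcomes measured at baseline are to be compared by t-test without baseline adjustment, and the plan names neither the scale nor the visit

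*Combined protocol and SAP*

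**What the plan says.** The Statistical analysis section has one sentence for every secondary outcome: "Comparisons of secondary parameters are done using t-tests or chi-square-tests (or their nonparametric equivalents if continuous data are not normally distributed". No section names a baseline covariate, ANCOVA, a repeated-measures model or an analysis visit for these outcomes.

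The baseline values exist. Data collection and outcome measures states: "Different lung function tests are performed at baseline, after two, four and six months to assess changes in lung function", and the same sentence goes on to diffusion capacity, NO and CO. On the questionnaires it says: "Changes in quality of life are assessed at baseline, after two, four, six months using different disease-specific questionnaires: SGRQ, CAT and ACT". It then adds: "To assess general quality of life, SF-36-questionnaire is used". Study design and procedures puts all four questionnaires on one schedule, "to assess quality of life at baseline, after two, four and six months".

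The adherence outcomes are different. Under Measurement of objective adherence, "Daily measurements are started after the baseline visit (T0) and are continued until the end of the study (visit T3", so they have no baseline value and this point does not apply to them.

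**The concern.** The Study objective section says the trial will "assess the effect of an acoustic reminder and a close supervision by a pharmacist on the adherence, course of diseases and quality of life". The sample size was set only for time to next exacerbation, so precision on lung function and quality of life is whatever that number of patients happens to give. A t-test that leaves out T0, or uses it only by subtraction, generally wastes information already collected.

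The sentence is also open. There are three follow-up visits and two possible scales, so up to six t-tests per outcome would fit the text, and the reader could not tell which was planned.

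Bias is not at stake, and neither is the conclusion on exacerbations.

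**Working it through.** **The plan's own figure.** The only power statement is for the primary outcome: 80% with 70 per group, HR 0.36, one-tailed 5%. It reproduces:

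- HR = ln(1 − 0.12) / ln(1 − 0.30) = 0.358.
- Expected events = 140 × (0.30 + 0.12)/2 = 29.4.
- Freedman's formula: √29.4 × (1 − 0.36)/(1 + 0.36) − 1.645 = 0.91, a power of about 82%.

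No figure is given for any secondary outcome.

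**Inputs for the check.** From Calculation of sample size: 70 per group. Assumed, because the documents do not give them: correlation r between T0 and follow-up from 0.3 to 0.9, equal SD at T0 and follow-up, complete cases, two-sided 5% and 80% power.

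**Variance of the group difference, relative to a t-test on the follow-up value:**

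- follow-up value: 1
- change score: 2(1 − r)
- ANCOVA on T0: 1 − r²

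So ANCOVA/change = (1 − r²)/[2(1 − r)] = (1 + r)/2, and ANCOVA/follow-up = 1 − r².

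| r | ANCOVA/change | CI narrower than change | ANCOVA/follow-up | n per arm for change score to match ANCOVA with 70 |
|---|---|---|---|---|
| 0.3 | 0.65 | 19% | 0.91 | 108 |
| 0.5 | 0.75 | 13% | 0.75 | 93 |
| 0.8 | 0.90 | 5% | 0.36 | 78 |
| 0.9 | 0.95 | 2.5% | 0.19 | 74 |

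The third column is 1 − √((1 + r)/2). The last is 70 / ((1 + r)/2).

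**Detectable difference in SD units** (noncentral t; 138 df for the t-tests, 137 for ANCOVA):

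| r | change score | follow-up value | ANCOVA |
|---|---|---|---|
| 0.3 | 0.564 | 0.477 | 0.455 |
| 0.5 | 0.477 | 0.477 | 0.413 |
| 0.8 | 0.302 | 0.477 | 0.286 |
| 0.9 | 0.213 | 0.477 | 0.208 |

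Study design and procedures mentions 169 participants. Split 85/84 with no losses, the figures at r = 0.5 are 0.434 SD for either t-test and 0.375 SD for ANCOVA. The relative gain is the same.

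**Simulation check** (20,000 runs, 70 per arm, true difference 0.4 SD). Power for change / follow-up / ANCOVA was 51.5% / 65.4% / 69.4% at r = 0.3, 65.5% / 66.0% / 77.8% at r = 0.5, and 96.1% / 65.4% / 97.4% at r = 0.8. The mean estimate was 0.40 for all three methods, so none is biased.

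**Unequal SDs.** With k = SD at T0 / SD at follow-up, ANCOVA/change = (1 − r²)/(1 + k² − 2kr). At r = 0.3, 0.5, 0.8 and 0.9 the variance reduction is 21.6%, 10.7%, 0% and 5.0% for k = 0.8, and 49.8%, 42.9%, 36.0% and 39.2% for k = 1.25. The gain vanishes when r = k, where the slope on T0 is 1. In large samples it is never negative.

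**Open visit and scale.** I took one outcome with no true effect and equal correlation across visits. If change is fixed as the scale but any of three visits may be chosen, the chance of at least one p < 0.05 is about 12% to 13%. If the scale is open as well (six tests), it is 19.5% to 21.7% for r from 0.9 down to 0.5. This shows what the text permits, not what the sponsor would do.

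**The case against.** The best defence is that the text speaks of *changes*, so the scale is largely settled. A t-test on change is valid and already uses T0, and its loss against ANCOVA may be trivial. At r = 0.9 the detectable difference moves only from 0.213 to 0.208 SD, and with r = k the gain is nil. Most of this stands. Change is the likelier reading for lung function, SGRQ, CAT and ACT. It is plausible for diffusion capacity, NO and CO, which share the lung-function sentence, and even for SF-36, whose sentence follows directly on the questionnaires. But the wording explains why the measurements are taken. It does not define a between-group endpoint, say to which visit the change runs, or link to the t-test. Since r is unknown, the adjusted analysis is the safe choice: in large samples it loses nothing and it may gain a good deal.

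Three smaller objections also have force:

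- Multiple imputation is already planned for data with less than 25% missing values. Within that limit the mixed model's use of incomplete patients is a side benefit, not a reason to prefer it.
- The inhalation-technique score is also recorded at T0 and at every later visit, so the same question arises there.
- The figures assume roughly normal data and do not describe the nonparametric tests that the plan allows.

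**Conclusion.** The concern holds. The planned test makes no adjustment for T0, and neither scale nor visit is fixed. The loss is in precision and pre-specification for secondary outcomes; there is no bias. With equal SDs and r from 0.3 to 0.9, all assumed, the adjusted analysis has 5% to 35% less variance than a change-score t-test and 9% to 81% less than a follow-up-value t-test. The gain over change scores is modest if r is high and depends on the ratio of SDs. The gap over the visit remains even where that gain is small. The sponsor should make the change, but the primary Cox analysis, the sample size and the conclusion on exacerbations do not depend on it.

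**What to change.** For lung function, diffusion capacity, NO, CO, SGRQ, CAT, ACT and SF-36, replace the t-test with one of:

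- ANCOVA at a named visit with the T0 value as covariate; or
- a mixed model over T1 to T3 with the T0 value as covariate and one named main contrast.

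Month 6, the end of follow-up, is an obvious choice of visit. For skewed measures use a transformation or rank ANCOVA so that the adjustment is kept; rank ANCOVA does not give a mean difference on the original scale. Say how the inhalation-technique score will be handled. Keep the two-sample comparison for the adherence outcomes. If t-tests are retained, state at least the scale and the visit.

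No new data or patients are needed. ANCOVA costs one degree of freedom and minor programming; the mixed model also needs visit terms, arm-by-visit terms and a covariance structure. The protocol says "Enrolment started on January 2014 and will end as soon as at least 154 individuals are included in the study", so the change belongs in a dated amendment made before any outcome data are examined by arm.
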